Appendix A

I80.232	Phlebitis and thrombophlebitis of left tibial vein
I80.233	Phlebitis and thrombophlebitis of tibial vein, bilateral
I80.239	Phlebitis and thrombophlebitis of unspecified tibial vein
I80.29	Phlebitis and thrombophlebitis of other deep vessels of lower extremities
I80.291	Phlebitis and thrombophlebitis of other deep vessels of right lower extremity
I80.292	Phlebitis and thrombophlebitis of other deep vessels of left lower extremity
I80.293	Phlebitis and thrombophlebitis of other deep vessels of lower extremity, bilateral
I80.299	Phlebitis and thrombophlebitis of other deep vessels of unspecified lower extremity
I80.3	Phlebitis and thrombophlebitis of lower extremities, unspecified
I80.9	Phlebitis and thrombophlebitis of unspecified site
I82.0	Budd-Chiari syndrome
I82.1	Thrombophlebitis migrans
I80.3	Phlebitis and thrombophlebitis of lower extremities, unspecified
I82.4	Acute embolism and thrombosis of deep veins of lower extremity
I82.40	Acute embolism and thrombosis of unspecified deep veins of lower extremity
I82.401	Acute embolism and thrombosis of unspecified deep veins of right lower extremity
I82.402	Acute embolism and thrombosis of unspecified deep veins of left lower extremity
I82.403	Acute embolism and thrombosis of unspecified deep veins of lower extremity, bilateral
I82.409	Acute embolism and thrombosis of unspecified deep veins of unspecified lower extremity
I82.41	Acute embolism and thrombosis of femoral vein
I82.411	Acute embolism and thrombosis of right femoral vein
I82.412	Acute embolism and thrombosis of left femoral vein
I82.413	Acute embolism and thrombosis of femoral vein, bilateral
I82.419	Acute embolism and thrombosis of unspecified femoral vein
I82.42	Acute embolism and thrombosis of iliac vein
I82.421	Acute embolism and thrombosis of right iliac vein
I82.422	Acute embolism and thrombosis of left iliac vein
I82.423	Acute embolism and thrombosis of iliac vein, bilateral
I82.429	Acute embolism and thrombosis of unspecified iliac vein
I82.43	Acute embolism and thrombosis of popliteal vein
I82.431	Acute embolism and thrombosis of right popliteal vein
I82.432	Acute embolism and thrombosis of left popliteal vein
I82.433	Acute embolism and thrombosis of popliteal vein, bilateral
I82.439	Acute embolism and thrombosis of unspecified popliteal vein
I82.44	Acute embolism and thrombosis of tibial vein

Appendix A

I82.441	Acute embolism and thrombosis of right tibial vein
I82.442	Acute embolism and thrombosis of left tibial vein
I82.443	Acute embolism and thrombosis of tibial vein, bilateral
I82.449	Acute embolism and thrombosis of unspecified tibial vein
I82.49	Acute embolism and thrombosis of other specified deep vein of lower extremity
I82.491	Acute embolism and thrombosis of other specified deep vein of right lower extremity
I82.492	Acute embolism and thrombosis of other specified deep vein of left lower extremity
I82.493	Acute embolism and thrombosis of other specified deep vein of lower extremity, bilateral
I82.499	Acute embolism and thrombosis of other specified deep vein of unspecified lower extremity
I82.4Y	Acute embolism and thrombosis of unspecified deep veins of proximal lower extremity
I82.4Y1	Acute embolism and thrombosis of unspecified deep veins of right proximal lower extremity
I82.4Y2	Acute embolism and thrombosis of unspecified deep veins of left proximal lower extremity
I82.4Y3	Acute embolism and thrombosis of unspecified deep veins of proximal lower extremity, bilateral
I82.4Y9	Acute embolism and thrombosis of unspecified deep veins of unspecified proximal lower extremity
I82.4Z	Acute embolism and thrombosis of unspecified deep veins of distal lower extremity
I82.4Z1	Acute embolism and thrombosis of unspecified deep veins of right distal lower extremity
I82.4Z2	Acute embolism and thrombosis of unspecified deep veins of left distal lower extremity
I82.4Z3	Acute embolism and thrombosis of unspecified deep veins of distal lower extremity, bilateral
I82.4Z9	Acute embolism and thrombosis of unspecified deep veins of unspecified distal lower extremity
I82.5	Chronic embolism and thrombosis of deep veins of lower extremity
I82.50	Chronic embolism and thrombosis of unspecified deep veins of lower extremity
I82.501	Chronic embolism and thrombosis of unspecified deep veins of right lower extremity
I82.502	Chronic embolism and thrombosis of unspecified deep veins of left lower extremity
I82.503	Chronic embolism and thrombosis of unspecified deep veins of lower extremity, bilateral
I82.509	Chronic embolism and thrombosis of unspecified deep veins of unspecified lower extremity
I82.51	Chronic embolism and thrombosis of femoral vein
I82.511	Chronic embolism and thrombosis of right femoral vein
I82.512	Chronic embolism and thrombosis of left femoral vein
I82.513	Chronic embolism and thrombosis of femoral vein, bilateral
I82.519	Chronic embolism and thrombosis of unspecified femoral vein
I82.52	Chronic embolism and thrombosis of iliac vein
I82.521	Chronic embolism and thrombosis of right iliac vein
I82.522	Chronic embolism and thrombosis of left iliac vein
I82.523	Chronic embolism and thrombosis of iliac vein, bilateral
I82.529	Chronic embolism and thrombosis of unspecified iliac vein

Appendix A

I82.53	Chronic embolism and thrombosis of popliteal vein
I82.531	Chronic embolism and thrombosis of right popliteal vein
I82.532	Chronic embolism and thrombosis of left popliteal vein
I82.533	Chronic embolism and thrombosis of popliteal vein, bilateral
I82.539	Chronic embolism and thrombosis of unspecified popliteal vein
I82.54	Chronic embolism and thrombosis of tibial vein
I82.541	Chronic embolism and thrombosis of right tibial vein
I82.542	Chronic embolism and thrombosis of left tibial vein
I82.543	Chronic embolism and thrombosis of tibial vein, bilateral
I82.549	Chronic embolism and thrombosis of unspecified tibial vein
I82.59	Chronic embolism and thrombosis of other specified deep vein of lower extremity
I82.591	Chronic embolism and thrombosis of other specified deep vein of right lower extremity
I82.592	Chronic embolism and thrombosis of other specified deep vein of left lower extremity
I82.593	Chronic embolism and thrombosis of other specified deep vein of lower extremity, bilateral
I82.599	Chronic embolism and thrombosis of other specified deep vein of unspecified lower extremity
I82.5Y	Chronic embolism and thrombosis of unspecified deep veins of proximal lower extremity
I82.5Y1	Chronic embolism and thrombosis of unspecified deep veins of right proximal lower extremity
I82.5Y2	Chronic embolism and thrombosis of unspecified deep veins of left proximal lower extremity
I82.5Y3	Chronic embolism and thrombosis of unspecified deep veins of proximal lower extremity, bilateral
I82.5Y9	Chronic embolism and thrombosis of unspecified deep veins of unspecified proximal lower extremity
I82.5Z	Chronic embolism and thrombosis of unspecified deep veins of distal lower extremity
I82.5Z1	Chronic embolism and thrombosis of unspecified deep veins of right distal lower extremity
I82.5Z2	Chronic embolism and thrombosis of unspecified deep veins of left distal lower extremity
I82.5Z3	Chronic embolism and thrombosis of unspecified deep veins of distal lower extremity, bilateral
I82.5Z9	Chronic embolism and thrombosis of unspecified deep veins of unspecified distal lower extremity
I82.6	Acute embolism and thrombosis of veins of upper extremity
I82.60	Acute embolism and thrombosis of unspecified veins of upper extremity
I82.601	Acute embolism and thrombosis of unspecified veins of right upper extremity
I82.602	Acute embolism and thrombosis of unspecified veins of left upper extremity
I82.603	Acute embolism and thrombosis of unspecified veins of upper extremity, bilateral
I82.609	Acute embolism and thrombosis of unspecified veins of unspecified upper extremity
I82.62	Acute embolism and thrombosis of deep veins of upper extremity
I82.621	Acute embolism and thrombosis of deep veins of right upper extremity
I82.622	Acute embolism and thrombosis of deep veins of left upper extremity
I82.623	Acute embolism and thrombosis of deep veins of upper extremity, bilateral

Appendix A

I82.629	Acute embolism and thrombosis of deep veins of unspecified upper extremity
I82.890	Acute embolism and thrombosis of other specified veins
I82.90	Acute embolism and thrombosis of unspecified vein
I82.A1	Acute embolism and thrombosis of axillary vein
I82.A11	Acute embolism and thrombosis of right axillary vein
I82.A12	Acute embolism and thrombosis of left axillary vein
I82.A13	Acute embolism and thrombosis of axillary vein, bilateral
I82.A19	Acute embolism and thrombosis of unspecified axillary vein
I82.B1	Acute embolism and thrombosis of subclavian vein
I82.B11	Acute embolism and thrombosis of right subclavian vein
I82.B12	Acute embolism and thrombosis of left subclavian vein
I82.B13	Acute embolism and thrombosis of subclavian vein, bilateral
I82.B19	Acute embolism and thrombosis of unspecified subclavian vein
I82.C1	Acute embolism and thrombosis of internal jugular vein
I82.C11	Acute embolism and thrombosis of right internal jugular vein
I82.C12	Acute embolism and thrombosis of left internal jugular vein
I82.C13	Acute embolism and thrombosis of internal jugular vein, bilateral
I82.C19	Acute embolism and thrombosis of unspecified internal jugular vein

Appendix A

Title

Major Bleeding

ICD-9 Dx inpatient any position

423	(ICD9) HEMOPERICARDIUM
430	(ICD9) SUBARACHNOID HEMORRHAGE
431	(ICD9) INTRACEREBRAL HEMORRHAGE
432	(ICD9) NONTRAUMATIC EXTRADURAL HEMORRHAGE
432.1	(ICD9) SUBDURAL HEMORRHAGE
432.9	(ICD9) UNSPECIFIED INTRACRANIAL HEMORRHAGE
459	(ICD9) HEMORRHAGE UNSPECIFIED
531	(ICD9) ACUTE GASTRIC ULCER WITH HEMORRHAGE
531	(ICD9) ACUTE GASTRIC ULCER WITH HEMORRHAGE WITHOUT OBSTRUCTION
531.01	(ICD9) ACUTE GASTRIC ULCER WITH HEMORRHAGE WITH OBSTRUCTION
531.2	(ICD9) ACUTE GASTRIC ULCER WITH HEMORRHAGE AND PERFORATION
531.2	(ICD9) ACUTE GASTRIC ULCER WITH HEMORRHAGE AND PERFORATION WITHOUT OBSTRUCTION
531.21	(ICD9) ACUTE GASTRIC ULCER WITH HEMORRHAGE AND PERFORATION WITH OBSTRUCTION
531.4	(ICD9) CHRONIC OR UNSPECIFIED GASTRIC ULCER WITH HEMORRHAGE
531.4	(ICD9) CHRONIC OR UNSPECIFIED GASTRIC ULCER WITH HEMORRHAGE WITHOUT OBSTRUCTION
531.41	(ICD9) CHRONIC OR UNSPECIFIED GASTRIC ULCER WITH HEMORRHAGE WITH OBSTRUCTION
531.6	(ICD9) CHRONIC OR UNSPECIFIED GASTRIC ULCER WITH HEMORRHAGE AND PERFORATION
531.6	(ICD9) CHRONIC OR UNSPECIFIED GASTRIC ULCER WITH HEMORRHAGE AND PERFORATION WITHOUT OBSTRUCTION
531.61	(ICD9) CHRONIC OR UNSPECIFIED GASTRIC ULCER WITH HEMORRHAGE AND PERFORATION WITH OBSTRUCTION
532	(ICD9) ACUTE DUODENAL ULCER WITH HEMORRHAGE
532	(ICD9) ACUTE DUODENAL ULCER WITH HEMORRHAGE WITHOUT OBSTRUCTION
532.01	(ICD9) ACUTE DUODENAL ULCER WITH HEMORRHAGE WITH OBSTRUCTION
532.2	(ICD9) ACUTE DUODENAL ULCER WITH HEMORRHAGE AND PERFORATION
532.2	(ICD9) ACUTE DUODENAL ULCER WITH HEMORRHAGE AND PERFORATION WITHOUT OBSTRUCTION
532.21	(ICD9) ACUTE DUODENAL ULCER WITH HEMORRHAGE AND PERFORATION WITH OBSTRUCTION
532.4	(ICD9) CHRONIC OR UNSPECIFIED DUODENAL ULCER WITH HEMORRHAGE
532.4	(ICD9) CHRONIC OR UNSPECIFIED DUODENAL ULCER WITH HEMORRHAGE WITHOUT OBSTRUCTION

Appendix A

532.41 (ICD9) CHRONIC OR UNSPECIFIED DUODENAL ULCER WITH HEMORRHAGE WITH OBSTRUCTION

532.6 (ICD9) CHRONIC OR UNSPECIFIED DUODENAL ULCER WITH HEMORRHAGE AND PERFORATION

532.6 (ICD9) CHRONIC OR UNSPECIFIED DUODENAL ULCER WITH HEMORRHAGE AND PERFORATION WITHOUT OBSTRUCTION

532.61 (ICD9) CHRONIC OR UNSPECIFIED DUODENAL ULCER WITH HEMORRHAGE AND PERFORATION WITH OBSTRUCTION

533 (ICD9) ACUTE PEPTIC ULCER OF UNSPECIFIED SITE WITH HEMORRHAGE

533 (ICD9) ACUTE PEPTIC ULCER OF UNSPECIFIED SITE WITH HEMORRHAGE WITHOUT OBSTRUCTION

533.01 (ICD9) ACUTE PEPTIC ULCER OF UNSPECIFIED SITE WITH HEMORRHAGE WITH OBSTRUCTION

533.2 (ICD9) ACUTE PEPTIC ULCER OF UNSPECIFIED SITE WITH HEMORRHAGE AND PERFORATION

533.2 (ICD9) ACUTE PEPTIC ULCER OF UNSPECIFIED SITE WITH HEMORRHAGE AND PERFORATION WITHOUT OBSTRUCTION

533.21 (ICD9) ACUTE PEPTIC ULCER OF UNSPECIFIED SITE WITH HEMORRHAGE AND PERFORATION WITH OBSTRUCTION

533.4 (ICD9) CHRONIC OR UNSPECIFIED PEPTIC ULCER OF UNSPECIFIED SITE WITH HEMORRHAGE

533.4 (ICD9) CHRONIC OR UNSPECIFIED PEPTIC ULCER OF UNSPECIFIED SITE WITH HEMORRHAGE WITHOUT OBSTRUCTION

533.41 (ICD9) CHRONIC OR UNSPECIFIED PEPTIC ULCER OF UNSPECIFIED SITE WITH HEMORRHAGE WITH OBSTRUCTION

533.6 (ICD9) CHRONIC OR UNSPECIFIED PEPTIC ULCER OF UNSPECIFIED SITE WITH HEMORRHAGE AND PERFORATION

533.6 (ICD9) CHRONIC OR UNSPECIFIED PEPTIC ULCER OF UNSPECIFIED SITE WITH HEMORRHAGE AND PERFORATION WITHOUT OBSTRUCTION

533.61 (ICD9) CHRONIC OR UNSPECIFIED PEPTIC ULCER OF UNSPECIFIED SITE WITH HEMORRHAGE AND PERFORATION WITH OBSTRUCTION

534 (ICD9) ACUTE GASTROJEJUNAL ULCER WITH HEMORRHAGE

534 (ICD9) ACUTE GASTROJEJUNAL ULCER WITH HEMORRHAGE WITHOUT OBSTRUCTION

534.01 (ICD9) ACUTE GASTROJEJUNAL ULCER WITH HEMORRHAGE WITH OBSTRUCTION

534.2 (ICD9) ACUTE GASTROJEJUNAL ULCER WITH HEMORRHAGE AND PERFORATION

534.2 (ICD9) ACUTE GASTROJEJUNAL ULCER WITH HEMORRHAGE AND PERFORATION WITHOUT OBSTRUCTION

534.21 (ICD9) ACUTE GASTROJEJUNAL ULCER WITH HEMORRHAGE AND PERFORATION WITH OBSTRUCTION

534.4 (ICD9) CHRONIC OR UNSPECIFIED GASTROJEJUNAL ULCER WITH HEMORRHAGE

Appendix A

534.4 (ICD9) CHRONIC OR UNSPECIFIED GASTROJEJUNAL ULCER WITH HEMORRHAGE WITHOUT OBSTRUCTION

534.41 (ICD9) CHRONIC OR UNSPECIFIED GASTROJEJUNAL ULCER WITH HEMORRHAGE WITH OBSTRUCTION

534.6 (ICD9) CHRONIC OR UNSPECIFIED GASTROJEJUNAL ULCER WITH HEMORRHAGE AND PERFORATION

534.6 (ICD9) CHRONIC OR UNSPECIFIED GASTROJEJUNAL ULCER WITH HEMORRHAGE AND PERFORATION
WITHOUT OBSTRUCTION

534.61 (ICD9) CHRONIC OR UNSPECIFIED GASTROJEJUNAL ULCER WITH HEMORRHAGE AND PERFORATION WITH
OBSTRUCTION

562.02 (ICD9) DIVERTICULOSIS OF SMALL INTESTINE WITH HEMORRHAGE

562.03 (ICD9) DIVERTICULITIS OF SMALL INTESTINE WITH HEMORRHAGE

562.12 (ICD9) DIVERTICULOSIS OF COLON WITH HEMORRHAGE

562.13 (ICD9) DIVERTICULITIS OF COLON WITH HEMORRHAGE

568.81 (ICD9) HEMOPERITONEUM (NONTRAUMATIC)

569.3 (ICD9) HEMORRHAGE OF RECTUM AND ANUS

569.83 (ICD9) PERFORATION OF INTESTINE

569.85 (ICD9) ANGIODYSPLASIA OF INTESTINE WITH HEMORRHAGE

569.86 (ICD9) DIEULAFOY LESION (HEMORRHAGIC) OF INTESTINE

578 (ICD9) HEMATEMESIS

578.1 (ICD9) BLOOD IN STOOL

578.9 (ICD9) HEMORRHAGE OF GASTROINTESTINAL TRACT UNSPECIFIED

719.1 (ICD9) HEMARTHROSIS

719.1 (ICD9) HEMARTHROSIS SITE UNSPECIFIED

719.11 (ICD9) HERARTHROSIS INVOLVING SHOULDER REGION

719.12 (ICD9) HEMARTHROSIS INVOLVING UPPER ARM

719.13 (ICD9) HEMARTHROSIS INVOLVING FOREARM

719.14 (ICD9) HEMARTHROSIS INVOLVING HAND

719.15 (ICD9) HEMARTHROSIS INVOLVING PELVIC REGION AND THIGH

719.16 (ICD9) HEMARTHROSIS INVOLVING LOWER LEG

719.17 (ICD9) HEMARTHROSIS INVOLVING ANKLE AND FOOT

719.18 (ICD9) HEMARTHROSIS INVOLVING OTHER SPECIFIED SITES

719.19 (ICD9) HEMARTHROSIS INVOLVING MULTIPLE SITES

784.7 (ICD9) EPISTAXIS

784.8 (ICD9) HEMORRHAGE FROM THROAT

Appendix A

599.7	(ICD9) HEMATURIA
599.7	(ICD9) HEMATURIA UNSPECIFIED
599.71	(ICD9) GROSS HEMATURIA
599.72	(ICD9) MICROSCOPIC HEMATURIA
786.3	(ICD9) HEMOPTYSIS
786.3	(ICD9) HEMOPTYSIS UNSPECIFIED
786.31	(ICD9) ACUTE IDIOPATHIC PULMONARY HEMORRHAGE IN INFANTS
786.39	(ICD9) OTHER HEMOPTYSIS

ICD-10 Dx inpatient any position

I31.2	(ICD10) Hemopericardium, not elsewhere classified
I60.00	(ICD10) Nontraumatic subarachnoid hemorrhage from unspecified carotid siphon and bifurcation
I60.01	(ICD10) Nontraumatic subarachnoid hemorrhage from right carotid siphon and bifurcation
I60.02	(ICD10) Nontraumatic subarachnoid hemorrhage from left carotid siphon and bifurcation
I60.10	(ICD10) Nontraumatic subarachnoid hemorrhage from unspecified middle cerebral artery
I60.11	(ICD10) Nontraumatic subarachnoid hemorrhage from right middle cerebral artery
I60.12	(ICD10) Nontraumatic subarachnoid hemorrhage from left middle cerebral artery
I60.2	(ICD10) Nontraumatic subarachnoid hemorrhage from anterior communicating artery
I60.30	(ICD10) Nontraumatic subarachnoid hemorrhage from unspecified posterior communicating artery
I60.31	(ICD10) Nontraumatic subarachnoid hemorrhage from right posterior communicating artery
I60.32	(ICD10) Nontraumatic subarachnoid hemorrhage from left posterior communicating artery
I60.4	(ICD10) Nontraumatic subarachnoid hemorrhage from basilar artery
I60.50	(ICD10) Nontraumatic subarachnoid hemorrhage from unspecified vertebral artery
I60.51	(ICD10) Nontraumatic subarachnoid hemorrhage from right vertebral artery
I60.52	(ICD10) Nontraumatic subarachnoid hemorrhage from left vertebral artery
I60.6	(ICD10) Nontraumatic subarachnoid hemorrhage from other intracranial arteries
I60.7	(ICD10) Nontraumatic subarachnoid hemorrhage from unspecified intracranial artery
I60.8	(ICD10) Other nontraumatic subarachnoid hemorrhage
I60.9	(ICD10) Nontraumatic subarachnoid hemorrhage, unspecified
I61.0	(ICD10) Nontraumatic intracerebral hemorrhage in hemisphere, subcortical
I61.1	(ICD10) Nontraumatic intracerebral hemorrhage in hemisphere, cortical
I61.2	(ICD10) Nontraumatic intracerebral hemorrhage in hemisphere, unspecified
I61.3	(ICD10) Nontraumatic intracerebral hemorrhage in brain stem

Appendix A

I61.4	(ICD10) Nontraumatic intracerebral hemorrhage in cerebellum
I61.5	(ICD10) Nontraumatic intracerebral hemorrhage, intraventricular
I61.6	(ICD10) Nontraumatic intracerebral hemorrhage, multiple localized
I61.8	(ICD10) Other nontraumatic intracerebral hemorrhage
I61.9	(ICD10) Nontraumatic intracerebral hemorrhage, unspecified
I62.00	(ICD10) Nontraumatic subdural hemorrhage, unspecified
I62.01	(ICD10) Nontraumatic acute subdural hemorrhage
I62.02	(ICD10) Nontraumatic subacute subdural hemorrhage
I62.03	(ICD10) Nontraumatic chronic subdural hemorrhage
I62.1	(ICD10) Nontraumatic extradural hemorrhage
I62.9	(ICD10) Nontraumatic intracranial hemorrhage, unspecified
K25.0	(ICD10) Acute gastric ulcer with hemorrhage
K25.2	(ICD10) Acute gastric ulcer with both hemorrhage and perforation
K25.4	(ICD10) Chronic or unspecified gastric ulcer with hemorrhage
K25.6	(ICD10) Chronic or unspecified gastric ulcer with both hemorrhage and perforation
K26.0	(ICD10) Acute duodenal ulcer with hemorrhage
K26.2	(ICD10) Acute duodenal ulcer with both hemorrhage and perforation
K26.4	(ICD10) Chronic or unspecified duodenal ulcer with hemorrhage
K26.6	(ICD10) Chronic or unspecified duodenal ulcer with both hemorrhage and perforation
K27.0	(ICD10) Acute peptic ulcer, site unspecified, with hemorrhage
K27.2	(ICD10) Acute peptic ulcer, site unspecified, with both hemorrhage and perforation
K27.4	(ICD10) Chronic or unspecified peptic ulcer, site unspecified, with hemorrhage
K27.6	(ICD10) Chronic or unspecified peptic ulcer, site unspecified, with both hemorrhage and perforation
K28.0	(ICD10) Acute gastrojejunal ulcer with hemorrhage
K28.2	(ICD10) Acute gastrojejunal ulcer with both hemorrhage and perforation
K28.4	(ICD10) Chronic or unspecified gastrojejunal ulcer with hemorrhage
K28.6	(ICD10) Chronic or unspecified gastrojejunal ulcer with both hemorrhage and perforation
K55.21	(ICD10) Angiodysplasia of colon with hemorrhage
K56.60	(ICD10) Unspecified intestinal obstruction
K57.01	(ICD10) Diverticulitis of small intestine with perforation and abscess with bleeding
K57.11	(ICD10) Diverticulosis of small intestine without perforation or abscess with bleeding
K57.13	(ICD10) Diverticulitis of small intestine without perforation or abscess with bleeding
K57.21	(ICD10) Diverticulitis of large intestine with perforation and abscess with bleeding

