1.3 Primary endpoint for replication

The primary outcome of the study was symptomatic, recurrent VTE

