1.5 Secondary endpoint for replication (assay sensitivity) and RCT finding

Major bleeding; RR = 0.90 (95% CI 0.76–1.07)

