6.3.1 Outcome variables

Primary Effectiveness outcomes of interest: (definitions provided in **Appendix A**):

- **Primary Outcome:** VTE

Safety outcomes of interest:

1. Major bleeding

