6.3.2 Study follow-up

Both as-treated (AT) and intention-to-treat (ITT) analyses will be conducted with treatment defined as the index drug on the day of cohort entry. Because adherence in the real-world databases is expected to be much worse than in the trial, the AT analysis is the **primary** analysis, as it targets the relative hazard of outcomes on treatment.

For the AT analyses, the follow-up will start the day after initiation of rivaroxaban and comparator and will continue until the earliest date of the following events:

- The first occurrence of the outcome of interest, unless otherwise specified for selected outcomes,
- The date of end of continuous registration in the database,
- End of the study period,
- Measured death event occurs,
- Nursing home admission
 - Nursing home admissions are considered a censoring event because the data sources utilized typically provide little to no data on a patient, particularly on drug utilization, after admission. We will utilize this as an exclusion reason for cohorts for the same reason.
- The date of drug discontinuation, defined as the date of the last continuous treatment episode of the index drug (rivaroxaban and comparator) plus a defined grace period (i.e., 10 days after the end of the last prescription's days' supply in main analyses).
- The date of augmentation or switching from exposure to comparator or vice versa or augmentation/switching to any other NOAC (e.g. switching from rivaroxaban to apixaban would be a censoring event);
 - A dosage change on the index treatment does not fulfill this criterion
 - An added treatment that is not part of the exposure or comparator group does not fulfill this criterion

For the intention-to-treat (ITT) analyses, the censoring based on the augmentation/switching and treatment discontinuation will be replaced with a maximum allowed follow-up time of 365 days.

7. Initial Feasibility Analysis

Action report name:

Optum- <https://bwh-dope.aetion.com/projects/details/1527/rwrs/66276>

MarketScan- <https://bwh-dope.aetion.com/projects/details/1653/rwrs/66277>

Medicare- <https://bwh-dope.aetion.com/projects/details/1525/rwrs/67892>

Date conducted: 02/24/2021

Complete Aetion feasibility analysis using age, sex, and CCI as the only covariates and the primary endpoint (Section 6.3.1) as the outcome. No measures of association will be computed nor will incidence rates stratified by treatment group.

- Report patient characteristics by treatment group

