Appendix A

Trial Name (with web links)	EINSTEIN PE
Trial Name (with pdf links)	EINSTEIN PE
NCT	NCT00439777
Therapeutic Area	Cardiology/Vascular Diseases
Study batch	NOACs
Brand Name	Xarelto
Generic Name	Rivaroxaban
Sponsor	Bayer Johnson & Johnson Pharmaceutical Research & Development, L.L.C
Year	2012
Measurable endpoint	Percentage of Participants With Symptomatic Recurrent Venous Thromboembolism [VTE] (i.e. the Composite of Recurrent Deep Vein Thrombosis [DVT] or Fatal or Non-fatal Pulmonary Embolism [PE]) Until the Intended End of Study Treatment
Exposure	Rivaroxaban
Comparator	Enoxaparin/VKA
Population	Patients of legal age who had acute symptomatic pulmonary embolism with or without deep-vein thrombosis
Trial finding	HR = 1.12 (95% CI 0.75 to 1.68)
No. of Patients	4,832 (2,419 in exposed arm)
Non-inferiority margin	HR = 2.0
Assay Sens. Endpoint (from trial)	Percentage of Participants With the Composite Variable Comprising Recurrent DVT, Non-fatal PE and All Cause Mortality Until the Intended End of Study Treatment
Finding for potential Assay Sens. Outcome from trial-	HR = 0.85 (95% CI 0.63 to 1.14)
Power	0.90. Assuming equal efficacy, a total of 88 events was calculated to give a power of 90% to prove that rivaroxaban is at least as effective as the comparator, considering a non-inferiority upper CI margin for the hazard ratio of 2.0 (two-sided $\alpha=0.05$). A mean incidence for the primary efficacy outcome of 3% was expected and an enrollment of at least 3000 patients was necessary

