Appendix A

Title

Venous Thromboembolism (VTE)

ICD-9 Dx inpatient primary position

PE

- 415.1 PULMONARY EMBOLISM AND INFARCTION
- 415.11 IATROGENIC PULMONARY EMBOLISM AND INFARCTION
- 415.19 OTHER PULMONARY EMBOLISM AND INFARCTION

DVT

- 451.1 PHLEBITIS AND THROMBOPHLEBITIS OF DEEP VEINS OF LOWER EXTREMITIES
- 451.11 PHLEBITIS AND THROMBOPHLEBITIS OF FEMORAL VEIN (DEEP) (SUPERFICIAL)
- 451.19 PHLEBITIS AND THROMBOPHLEBITIS OF OTHER
- 451.2 PHLEBITIS AND THROMBOPHLEBITIS OF LOWER EXTREMITIES UNSPECIFIED
- 451.81 PHLEBITIS AND THROMBOPHLEBITIS OF ILIAC VEIN
- 451.9 PHLEBITIS AND THROMBOPHLEBITIS OF UNSPECIFIED SITE
- 453 BUDD-CHIARI SYNDROME
- 453.1 THROMBOPHLEBITIS MIGRANS
- 453.2 EMBOLISM AND THROMBOSIS OF INFERIOR VENA CAVA
- 453.4 ACUTE VENOUS EMBOLISM AND THROMBOSIS OF DEEP VESSELS OF LOWER EXTREMITY
- 453.4 ACUTE VENOUS EMBOLISM AND THROMBOSIS OF UNSPECIFIED DEEP VESSELS OF LOWER EXTREMITY
- 453.41 ACUTE VENOUS EMBOLISM AND THROMBOSIS OF DEEP VESSELS OF PROXIMAL LOWER EXTREMITY
- 453.42 ACUTE VENOUS EMBOLISM AND THROMBOSIS OF DEEP VESSELS OF DISTAL LOWER EXTREMITY
- 453.5 CHRONIC VENOUS EMBOLISM AND THROMBOSIS OF DEEP VESSELS OF LOWER EXTREMITY
- 453.5 CHRONIC VENOUS EMBOLISM AND THROMBOSIS OF UNSPECIFIED DEEP VESSELS OF LOWER EXTREMITY
- 453.51 CHRONIC VENOUS EMBOLISM AND THROMBOSIS OF DEEP VESSELS OF PROXIMAL LOWER EXTREMITY
- 453.52 CHRONIC VENOUS EMBOLISM AND THROMBOSIS OF DEEP VESSELS OF DISTAL LOWER EXTREMITY
- 453.8 ACUTE VENOUS EMBOLISM AND THROMBOSIS OF OTHER SPECIFIED VEINS
- 453.82 ACUTE VENOUS EMBOLISM AND THROMBOSIS OF DEEP VEINS OF UPPER EXTREMITY
- 453.83 ACUTE VENOUS EMBOLISM AND THROMBOSIS OF UPPER EXTREMITY UNSPECIFIED
- 453.84 ACUTE VENOUS EMBOLISM AND THROMBOSIS OF AXILLARY VEINS
- 453.85 ACUTE VENOUS EMBOLISM AND THROMBOSIS OF SUBCLAVIAN VEINS
- 453.86 ACUTE VENOUS EMBOLISM AND THROMBOSIS OF INTERNAL JUGULAR VEINS
- 453.87 ACUTE VENOUS EMBOLISM AND THROMBOSIS OF OTHER THORACIC VEINS
- 453.89 ACUTE VENOUS EMBOLISM AND THROMBOSIS OF OTHER SPECIFIED VEINS

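### Appendix A's Major Bleeding list counts intestinal obstruction (K56.60) and intestinal perforation (569.83, K63.1) as major bleeds with no bleed in the label and no bleeding code required alongside

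*Combined protocol and SAP*

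**What the plan says.** Section 6.3.1 lists VTE as the primary outcome and major bleeding as the safety outcome. Its effectiveness line points to Appendix A: "Primary Effectiveness outcomes of interest: (definitions provided in" that appendix.

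**Major bleeding.** The Appendix A list applies to inpatient diagnoses in any position, in both ICD-9 and ICD-10. K56.60 is entered as "ICD10) Unspecified intestinal obstruction". Intestinal perforation is entered as 569.83 (ICD-9) and K63.1 (ICD-10). The list has no severity rule and no rule that a second code must confirm bleeding. Section 1.5 gives this endpoint the assay-sensitivity role: "Major bleeding; RR = 0.90", with interval 0.76 to 1.07.

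**VTE.** Section 1.3 states the target: "The primary outcome of the study was symptomatic, recurrent VTE". The Appendix A list applies to inpatient diagnoses in the primary position. It includes "453.5 CHRONIC VENOUS EMBOLISM AND THROMBOSIS OF DEEP VESSELS OF LOWER EXTREMITY" with its subcodes, and the corresponding ICD-10 block I82.5 to I82.5Z9.

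**Follow-up.** Under Section 6.3.2, "the follow-up will start the day after initiation of rivaroxaban and comparator". One of the stopping events is "The first occurrence of the outcome of interest, unless otherwise specified for selected outcomes".

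**The concern.** The code lists are the working endpoints. If a code names no bleed and nothing else is required, an admission for obstruction or perforation without bleeding is scored as a major bleed. Because the rule is any position, the code need not be the reason for admission. Follow-up for an outcome stops at its first occurrence, so a false event also hides a later true one in the same patient. Section 1.5 uses major bleeding as the check that the database study can recover a known trial result, and events that are not bleeds dilute that check.

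The chronic leg-vein codes raise a similar but weaker question. All patients enter with PE and about 46% of the matched cohort has baseline DVT (Appendix B: 46.4% warfarin, 45.8% rivaroxaban). A chronic code during follow-up can therefore record the known clot and not a recurrence. Error unrelated to treatment pulls the HR toward 1, which favours a non-inferiority conclusion only if the true HR exceeds 1.

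**Working it through.** **1. Does the bleeding list treat these codes like the others?** Counting the Appendix A labels:

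| Condition named as present | Bleeding also named | No bleeding named |
|---|---|---|
| Perforation | 36: ICD-9 ulcer 6 per stem × 4 stems = 24; ICD-10 ulcer (K25-K28, .2 and .6) = 8; K57.01, .21, .41, .81 = 4 | 569.83, K63.1 |
| Obstruction | 16: ICD-9 ulcer .01, .21, .41, .61 × 4 stems | K56.60 |

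The three codes are the only exceptions. The perforation pair appears in both coding systems. K56.60 appears only in ICD-10, so the endpoint also changes with the coding system. (K63.81 names no bleed either, but its ICD-9 partner 569.86 is labelled hemorrhagic, so it is not challenged.)

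**2. Does the VTE list treat chronicity consistently?** Chronic leg-vein entries: 4 under 453.5x and 41 from I82.5 to I82.5Z9. The 8 entries under 453.8x and the 28 from I82.6 to I82.C19 are all labelled acute. Some others (453.2, 453.9, 451.9, I80.9) carry no acuity label.

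**3. Reproduce the plan's power.** Inputs from Section 10: margin 2, HR 1.12, two-sided alpha 0.05, 1:1 matching, expected events E.

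P(non-inferior) = Φ( (√E / 2) × ln(2 / HR) − 1.96 )

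- Pooled, E = 457.68: 0.99999 (plan 0.999988934)
- Optum, E = 57.57: 0.5947 (plan 0.594735156)
- MarketScan, E = 168.89: 0.9647 (plan 0.964666171)
- Medicare, E = 233.42: 0.9932 (plan 0.993231623)

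The formula reproduces all four, so the power arithmetic itself is sound.

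**4. Effect of false VTE events.** The false share f is not in the documents; 2-5% is assumed, unrelated to treatment. The definition of f matters:

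- *Share of all events.* With true HR h, the false-to-true event ratio in the reference arm is k = f(1 + h) / [2(1 − f)], and HR_obs = (h + k) / (1 + k).
- *Share of reference-arm events.* HR_obs = (1 − f)h + f.

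At a true HR of 2.0 and E = 457.68 (nominal error 2.5%):

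| f | HR_obs, all events | False non-inferiority | HR_obs, reference arm | False non-inferiority |
|---|---|---|---|---|
| 2% | 1.970 | 3.6% | 1.980 | 3.2% |
| 5% | 1.927 | 5.9% | 1.950 | 4.6% |

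Example, f = 5% of all events: k = 0.05 × 3 / 1.90 = 0.0789; HR_obs = 2.0789 / 1.0789 = 1.927; 10.697 × ln(2 / 1.927) − 1.96 = −1.56; Φ = 0.059.

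At a true HR of 1.12 the observed HR is about 1.118 to 1.114 on either definition.

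**5. Effect on bleeding.** For assumed f = 2, 5 and 10%, 0.90(1 − f) + f = 0.902, 0.905 and 0.910. Taking f as a share of all events gives the same to within 0.001.

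**6. Power if 2-5% of VTE events are removed.** E is replaced by E(1 − f), with HR 1.12:

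- Pooled stays above 0.999.
- MarketScan: 0.965 to 0.962-0.957.
- Optum: 0.595 to 0.586-0.573.
- Medicare, on Section 10's 8,671 pairs: 0.993 to 0.992-0.991.

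The Section 9 censoring table sums to 31,786 patients, or 15,893 pairs. Less 2,153 and 5,675, that leaves 8,065 Medicare pairs, hence 16,130 × 13.46 / 1,000 = 217.1 events. On that count Medicare power is 0.990, falling to 0.988-0.986. That count conflict is a separate matter and does not change the conclusion here.

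**The case against.** **The pointer to Appendix A is on the effectiveness line only.** True: the safety line in Section 6.3.1 carries no pointer. But Appendix A contains a list titled Major Bleeding and the plan offers no other definition. The link is an inference, though a safe one.

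**The perforation pair may be deliberate.** This partly stands. 569.83 and K63.1 are listed in both systems, so they look less like a slip than K56.60. No rationale is given, and a co-recorded bleeding code would preserve any genuine bleeds among them.

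**The primary-position rule already screens the chronic codes.** This largely stands. The clot must be the main diagnosis of the admission, which should keep such events few. Nothing in the documents shows that a list without chronic codes performs better. Removing them would not cure the problem either: follow-up starts the day after initiation, so an acute code at readmission can still describe the index clot.

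**The numerical effect is small.** This also stands. The bleeding shift of at most 0.01 is minor against the trial interval 0.76 to 1.07. The VTE inflation is visible at a true HR of 2.0, which lies outside the interval 0.75 to 1.68 that Appendix A gives for the trial.

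**Stronger inferences a reader might draw.** One is that the lists bias the study materially toward non-inferiority; without counts by code the documents cannot show that, and the effect at the planned HR is negligible. Another is that microscopic hematuria, the repeated I80.3 or the absence of a named ICD-10 vena cava entry are errors of the same kind. Hematuria is at least a bleed, and its severity is a judgement. A repeated code changes no event. The vena cava entry is only something to check against 453.2.

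**Conclusion.** The point holds for the three bleeding codes, and it rests on the labels themselves: as written, obstruction or perforation without bleeding counts as a major bleed. The case is strongest for K56.60, which names no bleed and stands in one coding system only. The harm is mainly to what the endpoint means. Its importance also depends on Section 1.5, because the trial summary in Appendix A names a different assay-sensitivity endpoint ("HR = 0.85 (95% CI 0.63 to 1.14").

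The chronic leg-vein codes are a real but secondary inconsistency with a symptomatic, recurrent endpoint. They justify a prespecified analysis without those codes or a stated rationale; the documents do not establish that the narrower list must be primary.

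All magnitudes depend on the assumed false share and on error unrelated to treatment. Confidence is high on the code labels and low on the size. The change should be made, but the plan does not fail without it.

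**What to change.** Before the comparative analyses, while Section 13 is still blank:

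1. Delete K56.60 from the Major Bleeding list.
2. Delete 569.83 and K63.1, or count them only with a co-recorded bleeding code. Do not keep any of the three as a stand-alone bleed in a sensitivity analysis.
3. For VTE, prespecify an analysis without 453.5x and I82.5x. Alternatively, make that list primary and keep the current list as the sensitivity analysis. State the reason for the choice.
4. Report event counts by code group overall, not by arm, in keeping with Section 7's bar on treatment-stratified rates. Then rerun the event risk and power.
5. Optionally, state whether a severity rule applies to microscopic hematuria, and check I80.3 and the vena cava entry.

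The cost is a code-list edit and a rerun. The bleeding change does not touch VTE power. If the narrower VTE list is made primary and 2-5% of events drop out, pooled power is essentially unchanged. The visible loss is in Optum, which is already low at 0.595 and would fall to 0.586-0.573.
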